#### 9.2 Discussion of the clinical trial design, including control group selection

This is a multinational, multicenter, randomised, double-blind, placebo-controlled, parallel-group, clinical trial with the primary objective of evaluating the efficacy and safety of E6011 in patients with moderate to severe active Crohn's disease.

In Japan's Crohn's disease treatment guidelines, oral adrenocorticosteroids (including budesonide), nutritional therapy and immunomodulators are used as remission-induction therapy in moderate to severe

Date: 18-Apr-2022 version 11.0 Confidential Page 27 of 80

active Crohn's disease. Antibacterial drugs and apheresis are sometimes used as concomitant therapies. If oral adrenocorticosteroids and nutritional therapy are not effective, the use of anti-TNF $\alpha$  antibody biologics is recommended on the other hand, ECCO guidelines suggest using vedolizumab, an anti- $\alpha$ 4 $\beta$ 7 integrin antibody, as well as anti-TNF $\alpha$  antibody as biologics for the treatment of active Crohn's disease Recently, ustekinumab, an anti-IL-12/23 antibody, is beginning to be used as a drug indicated for Crohn's disease. As such, this clinical trial will be conducted to evaluate the efficacy of E6011 administration in patients with moderate to severe active Crohn's disease who were not deriving satisfactory benefits from the use of existing drugs (adrenocorticosteroids, immunomodulative drugs, or biologics).

In this clinical trial, randomisation is to take place to eliminate bias in allocating subjects to treatment groups, to maintain balance in subject characteristics between the groups, and in order to improve validity of statistical comparison of the groups. Further, stratified allocation is to be performed in which race and history of biologic use, which might influence the efficacy evaluation, are used as allocation factors. In order to minimise the possibility of bias in data collection and endpoint evaluation, treatment groups are to be blinded.

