### 9.4.3 Method of allocating subjects to treatment groups

A screening test is to take place within 42 days prior to the start on IMP administration, and patients whose eligibility has been confirmed are to be allocated to the E6011 10 mg/kg group or placebo group at a ratio of 1:1 using stratified allocation in which race and history of previous use of biologic medications are used as allocation factors.

Randomisation is to be performed by a central allocation method using an Interactive Web Response System (IWRS). At Week 0, the Principal Investigator (or his/her representative) is to enter the subjects' information into the IWRS. After subject registration is complete in the IWRS, the confirmation of registration (not including the information on group allocation) are to be notified via an e-mail to the Principal Investigator (or his/her representative), unblinded staff and Sponsor. Access to IWRS is to be restricted so that information on group allocation can be only retrieved by the unblinded trial staff of the Clinical Trial Centre and the unblinded trial staff of the Sponsor. The Principal Investigator or Sub-investigator is to record the eligibility results in the screening log/enrolment log, and prescribe the IMP to subjects deemed eligible to participate at screening and baseline evaluation.

After confirming the prescription by the Principal Investigator or Sub-investigator, the unblinded trial staff is to validate the registration results and allocation groups in the IWRS, and the unblinded trial pharmacist or unblinded trial doctor is to prepare the IMP in accordance with the treatment group allotment indicated by IWRS.

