3.2 Planned Study Design

This is a multinational, multicenter, randomized, double-blind, placebo-controlled, parallel-group, early phase 2 clinical trial. This clinical trial consists of a screening period, remission-induction period (double blind), rescue period (open-label), extension period (open-label), post-observation period and follow-up period. Administration of the IMP is to start after confirming eligibility at baseline (at week 0 before the start of the IMP administration) upon having carried out the screening test within 42 days prior to the start of the IMP administration after obtaining consent.

Patients with moderate to severe active Crohn's disease are to be randomly allocated to an E6011 10mg/kg group and a placebo group (1:1) using stratified allocation in which race (Japanese/non-Japanese) and history of previous use of biologics (yes/no) are used as allocation factors. The administration volume (about 100 mL) is to be prepared based on the weight of the subject by diluting E6011 with a physiological saline solution and infused intravenously over approximately 30 minutes. The physiological saline solution used to dilute E6011 is to be used as a placebo. The remission-induction period is to last 12 weeks, with E6011 or placebo administered in a double-blind method on Week 0, Week 1, Week 2, and once every two subsequent weeks up to Week 10, and the efficacy of E6011 is to be evaluated in Week 12. Subjects with a reduction in the CDAI of 70 or more (responders) compared to baseline at evaluation on Week 12 are to move on to the open-label extension period. The extension

period is to last 40 weeks, with 10 mg/kg of E6011 administered every four weeks from Week 12 to Week 48 and E6011 efficacy is to be evaluated at Week 52.

[figure not shown]

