6.1 General Methods

The analysis of the present study will be exploratory and primarily make use of descriptive statistical methods. In addition, exploratory statistical testing and modelling will be used to highlight interesting aspects of the data.

The continuous variables will be summarized using the following descriptive statistics:

- Number of patients (Number)
- Mean
- Standard deviation (SD)
- Median
- Minimum (min)
- Maximum (Max)
- Quartile 1 (Q1)
- Quartile 3 (Q3)
- Number of missing data (Missing)

Changes from baseline will be presented with its 95% confidence intervals.

For categorical variables including binary variables, the absolute (n) and relative frequency (%) will be summarized for each category at each scheduled visit.

All tables will be summarized by Japanese race.

Additionally, when appropriate, tables of efficacy endpoints (CDAI, PRO2 and SES-CD) in the remission-induction period will be summarized by:

- Sex: Male; Female
- Age: <35, 35-<50, ≥50
- Previous biologics: Yes; No.
- Prior biologic treatment used of Crohn's disease: Biologic naïve; 1 prior biologic failure; 2 prior biologic failures; ≥3 prior biologic failures
- CD-Type: Small intestine-type; Large intestine-type; Small and large intestine-type.
- CD duration: ≤5 years; > 5 years.
- CD-related surgery: Yes; No.
- Corticosteroids concomitant before randomization : Yes; No.
- Immunomodulators concomitant before randomization : Yes; No.
- Enteral nutrition concomitant before randomization : Yes; No.
- Baseline CDAI: ≤330; > 330.
- Baseline PRO2: ≤24; > 24.
- Baseline SES-CD: ≤15; > 15.

If one of the subgroups above has less than 5 patients, no results will be displayed.

Tables for adverse events in the remission-induction period will be summarized by:

- Sex: Male; Female
- Proclivity to hypohepatia: Yes, No
- Baseline eGFR: <30, 30-<60, 60-<90, ≥90

Five periods are defined in the study:

- 1) Remission-Induction Period (blind): comprises from day 0 to week 12. Subjects who were deemed eligible to participate in the screening period and at baseline are to be allocated to the E6011 10 mg/kg group and placebo group at the ratio of 1:1 using stratified allocation in which race and history of previous use of biologics are used as allocation factors. E6011 or placebo is to be administered to allocated subjects in a double-blind method on Week 0, Week 1, Week 2, and every two subsequent weeks until Week 10.

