6.8.1 Primary Efficacy analysis

Primary analysis aims to determine if the treatment effect in CR100 response rate at Week 12 is expected to be higher for patients treated with E6011 than for patients treated with placebo.

The Bayesian posterior distribution of the difference in the CR100 rate at Week 12 between E6011 (p1) and placebo (p2) is obtained as p1-p2 posterior distributions. Non-informative prior (Jeffreys) Beta (1/2, 1/2) distributions described by (Oleksandr Sverdlov, Yevgen Ryeznik, & Sheng Wu, January 1, 2015) will be used to calculate p1 and p2 posterior distributions.

A MCMC algorithm will be performed using the following parameters:

- Number of chains = 3
- Initial values for the algorithm in every chain= 3 starting values simulated by a Beta (0.5, 0.5)
- Number of Burn-in = 100000

- Number of Iterations = 200000

Diagnostic for the MCMC convergence will be checked through the Geweke Diagnostics test, Raftery-Lewis Diagnostics, Gelman-Rubin convergence and the autocorrelation efficiency. In case of any issue due to an autocorrelation or non-convergence of the algorithm, the size of the burn-in, the number of iterations and a possible thinning will be evaluated.

Efficacy of E6011 will be confirmed if there was a 50% or more probability of the difference between both groups being 25% according to the posterior distribution.

Probability of the difference between groups being greater than zero will be also calculated.

Subjects with missing primary endpoint data due to premature discontinuation before 12 weeks after administration, or other reasons are treated as non-responders (NRI) in the modeling of the endpoint.

Primary analysis will be performed in the FAS population, and in the PPS population as a supportive analysis.

Two sensitivity analysis will be performed a Last Observation Carried Forward (LOCF) and an Observed Case (OC) imputation for CDAI at week 12 will be used instead of NRI.

Another supportive analysis will be performed following the same logistic regression model (randomization strata and treatment group as fixed factor) used in the secondary analysis.

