6.8.2 Secondary Efficacy analysis

- a. CDAI response rate (CR70) and remission rate at week 12 will be analyzed using logistic regression model considering randomization strata (Japanese/Non-Japanese and Male/Female) and treatment group as fixed factor. This model will estimate the Odds Ratio between the treatment arms.

Also, the CDAI response rate (CR70, CR100) and remission rate are also to be described by treatment group week 2, week 4, week 8 and week 12.

And finally, CDAI, change and percentage change from baseline will be descriptively analyzed too by treatment group at baseline, week 2, week 4, week 8 and week 12.

- b. PRO2 response rate (PRO2-CR5, PRO2-CR8) and remission rate at week 12 will be analyzed using logistic regression model considering randomization strata (Japanese/Non-Japanese and Male/Female) and treatment group as fixed factor. This model will estimate the Odds Ratio between the treatment arms.

Also, the PRO2 response rate (PRO2-CR5, PRO2-CR8) and remission rate are also to be described by treatment group week 2, week 4, week 8 and week 12.

And finally, PRO2, change and percentage change from baseline will be descriptively analyzed too by treatment group at baseline, week 2, week 4, week 8 and week 12.

- c. SES-CD endoscopic response rate and endoscopic remission rate at week 12 will be analyzed using logistic regression model considering randomization strata (Japanese/Non-Japanese and Male/Female) and treatment group as fixed factor.
Also, the SES-CD endoscopic response rate and remission rate are also to be described by treatment group week 2, week 4, week 8 and week 12.
And finally, SES-CD endoscopic, change and percentage change from baseline will be descriptively analyzed too by treatment group at baseline, week 2, week 4, week 8 and week 12.
- d. Steroid-free CDAI response rate (CR70, CR100) and remission rate will be described by treatment group at week 2, week 4, week 8 and week 12.
- e. Steroid-free PRO2 response rate (PRO2-CR5, PRO2-CR8) and remission rate will be described by treatment group at week 2, week 4, week 8 and week 12.
- f. The dose of adrenocorticosteroids related to Crohn's disease will be described using the change and percentage change from baseline by treatment group at baseline, week 2, week 4, week 8 and week 12.

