The dose at baseline is calculated as the sum of doses in mg/day of all adrenocorticosteroids that are taken the baseline day. Doses at every visit are calculated as the sum of all adrenocorticosteroids taken from previous time point to the current visit date, for example, dose at week 2 is the sum of all doses taken from baseline to week 2 date.

Adrenocorticosteroids related to Crohn's disease will be identified as any concomitant corticosteroid at remission induction period in the database that has reported in the eCRF an indication to primary disease (Crohn's disease). Steroid free patients will be identified as patients that are taking any adrenocorticosteroid related to Crohn's disease at baseline and they stop taking them before week 12.

Subjects with missing secondary endpoint data due to premature discontinuation before 12 weeks after administration, or other reasons are treated as non-responders (NRI) in the modeling of the endpoints.

Secondary analysis will be performed in the FAS population and in the PPS population.

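### The secondary logistic models name sex as a randomisation stratum and leave out previous biologic use, the factor actually used

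*SAP*

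**What the plan says.** SAP 6.8.2 specifies the same model three times, under a (CDAI), b (PRO2) and c (SES-CD): a "logistic regression model considering randomization strata (Japanese/Non-Japanese and Male/Female) and treatment group as fixed factor". SAP 6.8.1 adds a supportive analysis of Week 12 CR100 that follows the "same logistic regression model (randomization strata and treatment group as fixed factor) used in the secondary analysis".

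The allocation is described differently everywhere else. SAP 3.2 has "stratified allocation in which race (Japanese/non-Japanese) and history of previous use of biologics (yes/no) are used as allocation factors", and SAP 6.1 has "stratified allocation in which race and history of previous use of biologics are used as allocation factors". Protocol 9.4.3 has "stratified allocation in which race and history of previous use of biologic medications are used as allocation factors", and protocol 9.1 and 9.1.2 agree. Protocol 9.2 gives the reason for the choice: "race and history of biologic use, which might influence the efficacy evaluation, are used as allocation factors".

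On where the models are run, SAP 6.8.2 states: "Secondary analysis will be performed in the FAS population and in the PPS population".

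**The concern.** The model text calls sex a randomisation stratum. Nothing in either document makes it one; in the SAP it is a demographic variable and a subgroup. The second real factor, previous biologic use, is missing from every planned regression for efficacy, although the protocol stratified on it because it might affect the outcome.

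Two things follow. Tables would be labelled as adjusted for the randomisation strata when they are adjusted for only one of the two. And a programmer must either follow text that is wrong or depart from it without a record, which in a 25-patient trial adds an undocumented analyst choice to every model-based odds ratio.

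**Working it through.** **1. Factors side by side**

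| Place | First factor | Second factor |
|---|---|---|
| Protocol 9.1, 9.1.2, 9.2, 9.4.3 | race | previous biologic use |
| SAP 3.2, 6.1 | race | previous biologic use |
| SAP 6.8.2 a, b, c | race | sex |

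The contradiction lies within the SAP, so it does not depend on which protocol version the SAP followed.

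**2. Models affected.** Part a covers 2 endpoints (CR70, CDAI remission), b covers 3 (PRO2-CR5, PRO2-CR8, PRO2 remission) and c covers 2 (endoscopic response, endoscopic remission). That is 2 + 3 + 2 = 7 secondary models, and 7 × 2 = 14 fits over FAS and PPS. The supportive CR100 model is the eighth.

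**3. The plan's own figure.** The only stated operating characteristic is a probability above 80% of confirming efficacy with 20 per group and a 40-point true difference. Exact enumeration of the Bayesian rule with Jeffreys priors gives 80.7% to 87.4% over placebo rates from 5% to 60%, so it reproduces. That analysis has no covariates and is untouched by this error.

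**4. Effect on the odds ratio.** The documents give no response rates by biologic history, so these are assumptions: 30% placebo response in experienced patients, 30% to 60% in naive patients, race and sex not prognostic. The naive share is 8/40 = 20% (protocol 9.3, a rough estimate). With weights w and placebo rates p0, the odds ratio without the factor is

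odds(Σ w·expit(logit p0 + log OR)) / odds(Σ w·p0).

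For OR 5 and 60% in naive patients, the treated rate is 0.2 × 0.882 + 0.8 × 0.682 = 0.722 (odds 2.596) and the placebo rate is 0.2 × 0.60 + 0.8 × 0.30 = 0.36 (odds 0.5625). The ratio is 4.62.

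| Naive placebo response | 30% | 40% | 50% | 60% |
|---|---|---|---|---|
| OR 5 becomes | 5.00 | 4.94 | 4.80 | 4.62 |
| OR 3 becomes | 3.00 | 2.98 | 2.91 | 2.82 |

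The largest shift is log(5/4.615) = 0.080. At a naive share of 10% it is 0.045, and at 30% it is 0.106.

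For scale, with an assumed 8/13 versus 3/12 responders the standard error of the log odds ratio is √(1/8 + 1/5 + 1/3 + 1/9) = 0.877. The shift is 0.080/0.877, about 9% of one standard error.

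**5. Whether the subgroup tables fill the gap.** SAP 6.1 tabulates efficacy by previous biologics, but "If one of the subgroups above has less than 5 patients, no results will be displayed". Protocol 9.7.2 reports 25 enrolled, and 20% of 25 is 5. If the naive count is Binomial(25, 0.20), P(fewer than 5) = 42%; it is 68% at a 15% share and 21% at 25%. The rule does not say whether the count is overall or per arm. Counted per arm, 5 naive patients split 2 and 3 would always be suppressed.

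**6. Sparse data after the correction.** With 5 naive patients, nt treated and nc on placebo (2 + 3 and 3 + 2 averaged), the chance that all or none respond is p1^nt·p0^nc + (1−p1)^nt·(1−p0)^nc. With a treatment OR of 5 this is 5% at a naive placebo response of 30%, 21% at 60%, and 26% for a rare endpoint at 10%. With no treatment effect and a 10% rate it is 0.9⁵ + 0.1⁵ = 59%. In those datasets ordinary logistic regression cannot estimate the biologic coefficient.

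A simulation (4,000 trials per setting, 25 patients, 5 naive, 25% placebo rate, true OR 5.57, biologic effect OR 1, 3 or 6) gave non-convergence of 8%, 8% and 6% with race and sex, against 11%, 16% and 29% with race and biologic use.

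**The case against.** The strongest reply is that little depends on these models. The primary rule has no covariates, SAP 6.1 calls the analysis exploratory, and no decision attaches to any of the eight odds ratios. The attenuation needs an assumed prognostic effect that the documents do not supply, and it is small even then. All of this stands, and it limits the weight of the point.

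SAP 6.8.1 does not itself list sex; read alone, its reference to randomisation strata is correct. It takes on the error only by reusing the secondary model. That is so, but the reuse is explicit.

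Previous biologic use is not ignored, since it defines subgroup tables, and the display rule reads most naturally as an overall count. That is fair. The 42% risk of suppression uses the overall count, although it rests on a rough estimate of the naive share.

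Swapping the covariate makes fitting less stable. This also stands, with a qualification: when all or none of the naive patients respond, the treatment odds ratio remains estimable from the experienced patients if their data allow. Nor should the correction be justified by power. In the 25-patient simulation the gain, among fits that converged, appeared even when biologic use had no effect (46% against 49%).

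None of this makes the present text right. A deliberate choice of sex as a covariate would not be called a randomisation stratum.

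**Conclusion.** The concern holds. Seven secondary models and the supportive CR100 model use race and a factor that was not used in the allocation, and omit one that was. This rests on the text alone and needs no assumption.

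The consequence is modest: mislabelled output and a missing covariate in exploratory models. If biologic history is prognostic and balanced between arms, the omission pulls the expected odds ratio towards 1, so it does not exaggerate efficacy on average; if it is not prognostic, the expected estimate does not move. The sizes depend on assumed response rates and a naive share taken from a rough planning estimate. It should be fixed, but it does not threaten the primary conclusion.

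**What to change.** Make these changes before the remission-induction database is unblinded. The documents do not give that date. If it has passed, record the correction and its timing in the Clinical Study Report, as protocol 9.7.5 requires for changes to the analysis plan.

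1. In SAP 6.8.2 a, b and c, give the strata as Japanese/non-Japanese and previous biologic use yes/no.
2. In SAP 6.8.1, name the same two factors for the supportive CR100 model.
3. If sex is wanted, list it as an additional covariate with a reason, not as a stratum.
4. Name Firth or exact logistic regression as the fallback under separation. With about 5 naive patients this belongs with the correction.
5. Minor: protocol 9.7.1.6.2 plans only rates and summary statistics for the secondary endpoints, while SAP 6.11 declares no modifications. Note the added logistic models there, after checking protocol v10, on which the SAP says it is based; only v11.0 was available for this comparison.

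The cost is wording in five places (6.8.1; 6.8.2 a, b and c; 6.11) and one model statement. Both factors are already collected for allocation, so no new data are needed.

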# 9.7.2 Target sample size

The number of subjects in this clinical trial was determined considering stimulation-generated operating characteristics relating to efficacy assessment, based on efficacy outcomes of the 101 trial and of similar drugs. With 20 subjects allotted to each group, if the actual difference in CR100 response rate between the E6011 group and placebo group is 40% or more, the probability of confirming the efficacy of E6011 is above 80%.

The number of enrolled subjects was 25 at the end of the recruitment. Therefore, the sample size will be reduced to 25 subjects, but the analysis plan will remain unchanged and performed in accordance with section 9.7 Statistical method.

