3.1 Study Population

Patients with Crohn's disease ranging from moderate to severe aged 18 or over and under 65 on the date of consent, diagnosed with small intestine-type, small and large intestine-type, or large intestine-type Crohn's disease at least 12 weeks before giving consent and that meet the rest of the inclusion/exclusion criteria

Approximately 40 subjects will be included in this clinical trial.

- E6011 group 20 subjects: Placebo group 20 subjects
- 22 Japanese subjects: 18 non-Japanese subjects (rough estimate)
- 8 biologic-naïve patients (rough estimate)

Subjects that meet all the following inclusion criteria and do not fall under any of the exclusion criteria shall receive the IMP.

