4.5.2 Secondary Endpoints for Efficacy

- CR70 response rate, CR100 response rate (excluding Week 12) and CDAI remission rate (proportion of subjects with below 150 points) at each evaluation time
- Proportion of subjects with at least 5-point reduction in PRO2 from baseline (PRO2-CR5 response rate), proportion of subjects with at least 8-point reduction from baseline (PRO2-CR8 response rate), and proportion of subjects with below 8 points (PRO2-remission rate) at each evaluation time
- Proportion of subjects with at least 50% improvement in SES-CD score from prior to IMP administration (endoscopic response rate) and proportion of subjects with 2 or less in SES-CD score (endoscopic remission rate) at Week 12
- Change and percent change in CDAI score from baseline at each evaluation time
- Change and percent change in PRO2 from baseline at each evaluation time
- Change and percent change in SES-CD score from baseline at Week 12
- In subjects who were concomitantly taking adrenocorticosteroid at remission induction period, proportion of subjects who achieved steroid-free maintenance (steroid-free remission rate, steroid-free improvement rate) through steroid dose reduction and clinical remission (CDAI remission or PRO2 remission) or clinical improvement (CR70 response, CR100 response, PRO2-CR5 response or PRO2-CR8 response)
- In subjects who were concomitantly taking adrenocorticosteroid at remission induction period, dosage (mg/day), change and percent change of adrenocorticosteroid from baseline.

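### With 25 patients, the SAP's logistic models may give no finite treatment odds ratio for low-rate endpoints, chiefly endoscopic remission, and no fallback is specified

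*SAP*

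**What the plan says.** SAP 6.8.2 models seven Week 12 endpoints: CR70, CDAI remission, PRO2-CR5, PRO2-CR8, PRO2 remission, endoscopic response and endoscopic remission. The model is a "logistic regression model considering randomization strata (Japanese/Non-Japanese and Male/Female) and treatment group as fixed factor". For the CDAI and PRO2 items the SAP adds "This model will estimate the Odds Ratio between the treatment arms". The SES-CD item has the same model without that sentence: "SES-CD endoscopic response rate and endoscopic remission rate at week 12 will be analyzed using logistic regression model". Missing outcomes count as non-response, and the secondary analyses are run in both the FAS and the PPS. SAP 6.8.1 applies the model to CR100 as a supportive analysis.

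Endoscopic remission is defined in SAP 4.5.2 as the "proportion of subjects with 2 or less in SES-CD score (endoscopic remission rate) at Week 12". Entry requires an SES-CD of at least 7, or at least 4 in the ileum for isolated ileal disease.

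Protocol 9.7.2 states "The number of enrolled subjects was 25 at the end of the recruitment", that "the sample size will be reduced to 25 subjects", and that the analysis plan does not change. SAP 3.1 still reads "Approximately 40 subjects will be included in this clinical trial".

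The SAP names no estimation method for the logistic models and gives no penalised, exact or other fallback for empty cells. Its non-convergence rules (6.8.1) concern the MCMC only. Its one small-number rule (6.1) suppresses subgroups of fewer than 5 patients.

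**The concern.** An unqualified logistic regression is normally fitted by maximum likelihood. If no patient in one arm responds, or all do, the likelihood keeps rising as the treatment coefficient moves towards infinity and no finite odds ratio exists. With two further factors, other sparse patterns (quasi-complete separation) do the same. Software then prints a very large or very small value, or a warning.

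Twelve or thirteen patients per arm leave little margin when events are rare. Low rates are plausible for endoscopic remission: it requires a fall from at least 7 (or 4) to 2 or less within 12 weeks, in patients whom existing treatment has not satisfied. Counting missing outcomes as non-response lowers rates further. At stake are the treatment-effect estimates that the SAP promises for these endpoints. Without a stated rule, the analyst who meets separation has to choose a remedy with the unblinded result in view.

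**Working it through.** **The plan's own figure.** The documents give no operating figure for these models. The only one they state is for the primary rule: above 80% probability of confirming efficacy with 20 per arm and a true 40-point difference. Using Jeffreys Beta(1/2, 1/2) priors and summing over all binomial outcomes, this probability is 80.7% to 84.9% for placebo rates of 5% to 50%, lowest at 70 v 30%. It reproduces, but says nothing about the logistic models.

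**Inputs.**
- 25 patients (Protocol 9.7.2). The 13 v 12 split is assumed from 1:1 allocation.
- Model: intercept, treatment, Japanese/non-Japanese, male/female (SAP 6.8.2).
- Japanese share: 22/40 = 55% (SAP 3.1).
- Male share: 60%, assumed.
- Response rates: assumed throughout.

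**Step 1: an arm with no responders or only responders.** For n patients at rate p, f(n, p) = (1-p)^n + p^n. The probability that at least one arm is affected is 1 - [1 - f(13, p1)] × [1 - f(12, p2)]. Two cases worked out:
- 30 v 10%: f is 0.0097 for E6011 and 0.2824 for placebo. The product 0.9903 × 0.7176 is 0.711, which leaves 0.289.
- 10 v 5%: f is 0.2542 for E6011 and 0.5404 for placebo. The product 0.7458 × 0.4596 is 0.343, which leaves 0.657.

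This is a lower bound for the planned model, because the covariates can only add ways to separate.

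**Step 2: the planned three-factor model.** Trials were simulated, and a linear-programming check showed whether the treatment coefficient itself is unbounded.

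| E6011 v placebo (assumed) | Step 1, exact | Step 2, treatment odds ratio non-finite |
|---|---|---|
| 55 v 30% | 1.4% | about 4% |
| 45 v 20% | 6.9% | 7-10% |
| 30 v 10% | 28.9% | about 30% |
| 20 v 5% | 56.6% | about 60% |
| 10 v 5% | 65.7% | 68-69% |

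**Step 3: effect of sample size.** Treatment odds ratio non-finite, same model:

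| Rates | 20 v 20 | 13 v 12 | 10 v 10 (illustrative PPS) |
|---|---|---|---|
| 5 v 5% | 58% | 78-80% | 85% |
| 20 v 10% | 16% | 32-34% | 45% |
| 60 v 20% | 2% | 10-12% | 21% |

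For rare endpoints the problem was present at the planned size. The smaller enrolment makes it worse.

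**Step 4: which coefficient fails.** The chance that some coefficient is infinite is higher than the chance that the treatment one is: 48-52% against 32-34% at 20 v 10%. If only a stratum term separates, the treatment odds ratio is still finite, so the treatment figure is the relevant one. Male/female is not an allocation factor; SAP 3.2 gives race and previous biologic use. That is a separate inconsistency. Putting biologic history (20% naive, from 8/40) in place of sex hardly moves the treatment figure (33% v 34% at 20 v 10%) but raises the any-coefficient figure (64% v 52%).

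**Step 5: does the remedy give an estimate?** Take 2/13 v 0/12. Maximum likelihood gives an infinite odds ratio. In the unadjusted two-group case the Firth fit amounts to adding 0.5 to each cell. The odds are then 2.5/11.5, or 0.217, for E6011 and 0.5/12.5, or 0.040, for placebo, and their ratio is 5.4. If nobody responds in either arm, the penalty alone drives the estimate. That has probability 0.95^25 = 28% at 5 v 5% and 0.90^25 = 7% at 10 v 10%, so it needs its own rule.

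**The case against.** The strongest reply is that little depends on these odds ratios. SAP 6.1 calls the analysis exploratory and primarily descriptive. SAP 6.8.2 also describes the rates by arm, Protocol 9.7.1.6.2 plans only descriptive secondary summaries, and no decision rule uses the models. The primary analysis has a proper Jeffreys prior, so its posterior always exists. All of this stands and limits the consequence. It does not supply the model-based estimates that the SAP adds, or a rule for when they fail.

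A reader might infer that the secondary models will often fail across the board, or that the planned secondary estimates will not exist. The documents do not support either reading. They give no secondary-endpoint rates. At the settings tried with both arms at 20% or more, failure in the FAS is about 1 in 8 or less, and CR70, PRO2-CR5 and PRO2-CR8 may well lie there. The odds-ratio sentence is attached to the CDAI and PRO2 items, not to endoscopy, where the risk is greatest. Quoting the chance that any coefficient separates would also overstate the risk to the treatment effect.

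Maximum likelihood is the usual reading of the SAP's wording but is not stated, and the SAP names neither a Wald interval nor a SAS procedure for these models. Exact logistic regression would be a defensible alternative to Firth.

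**Conclusion.** The point holds for low-rate endpoints. If an arm's true rate is about 10% or lower, the chance of a non-finite treatment odds ratio is roughly 30% or more at the settings tried, and 60-70% at 10-20 v 5%. For common response endpoints it is a minor risk in the FAS and a larger one in a reduced PPS. Endoscopic remission is the clearest candidate; CDAI and PRO2 remission are possible ones. These sizes rest on assumed response rates, a 13 v 12 split, 60% male, and a maximum-likelihood fit. This is a cheap improvement rather than a threat to the trial's main conclusion. Confidence is moderate, because the frequency depends on rates that the documents do not give.

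**What to change.** In SAP 6.8.2, and for the supportive CR100 model in 6.8.1:
- Fit the logistic models by Firth penalised likelihood with profile-likelihood intervals, in both FAS and PPS.
- Report the risk difference with its interval beside each odds ratio. This stays interpretable with sparse data and is on the scale of the primary analysis.
- When neither arm has a responder, or all patients respond, report only the rates and the risk difference.

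The change should be fixed before the remission-induction database is unblinded. If that has already happened, it should be reported as a post-unblinding change. The cost is a few SAP sentences and minor programming. The downside is slight shrinkage of the odds ratio.
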